7.5 Disease Assessment

If CT scan with contrast is contraindicated (except for chest CT scan), a MRI may be used as an alternative method of baseline disease assessment. If a chest CT scan with contrast is contraindicated, a chest CT scan without contrast should be performed.

The method used to document baseline status should be used consistently throughout study to facilitate comparison of scan results. Assessments must be performed on a calendar schedule and should not be affected by dose interruptions or delays. Refer to the Time and Events Table (Section 7.1) for the schedule of disease assessments.

7.5.1 Disease Assessment for Solid Tumor Histologies

Disease assessment for solid tumor types (ATC, BTC, GIST, NSGCT/NGGCT, WHO Grade 1 and 2 gliomas, WHO Grade 3 and 4 gliomas and ASI) will be conducted as noted below. For subjects whose disease may be followed by well-characterized tumor markers, disease assessment should also include results of tumor marker measurements.

Disease assessments will be completed as indicated in the Time and Events Table (Section 7.1).

Please refer to the IAG for additional details on imaging assessments for this study.

Baseline Assessments: The following baseline disease assessments are required for all subjects within 28 days prior to enrollment (or within 35 days if MRI is used for disease assessment):

Histology	Area(s) of Assessment	Imaging to be Performed	Alternative Imaging Methods if Contraindications are Present
ATC ¹	Brain	MRI with contrast	1 st alternative: MRI without contrast 2 nd alternative: CT scan with contrast
	Neck	CT scan with contrast	1 st alternative: a MRI with contrast 2 nd alternative: CT scan without contrast (if 1 st alternative is contraindicated)
	Chest/Abdomen (including liver and adrenal glands)	CT scan ²	N/A
BTC/ASI	Chest/Abdomen/Pelvis	CT scan with contrast	CT scan without contrast of the Chest and MRI with contrast of Abdomen/Pelvis
NSGCT/NGGCT	Chest/Abdomen/Pelvis	CT scan with contrast	CT scan without contrast of the Chest and MRI with contrast of Abdomen/Pelvis
GIST	Chest/Abdomen/Pelvis	CT scan with contrast	CT scan without contrast of the Chest and MRI with contrast of Abdomen/Pelvis
ATC ¹ BTC GIST NSGCT/NGGCT ASI WHO Grade 1-4 Glioma	Regions with known or suspected metastatic lesions	CT scan, MRI, or bone scan as appropriate	N/A
WHO Grade 1- 4 Glioma	Brain	MRI with contrast ³	N/A
NSGCT/NGGCT ⁴	Brain (for pituitary GCT)	MRI with contrast	1 st alternative: MRI without contrast 2 nd alternative: CT scan with contrast

Abbreviations: ASI, adenocarcinoma of small intestine; ATC, anaplastic thyroid carcinoma; BTC, biliary tract carcinoma; CNS, central nervous system; CR, complete response; CT, computed tomography; GCT, germ cell tumor; GIST,

gastrointestinal stromal tumor; MRI, magnetic resonance imaging; NGGCT, non-geminomatous germ cell tumor; NSGCT, non-seminomatous germ cell tumor; PET, positron emission tomography; SPM, Study Procedures Manual; WHO, World Health Organization

1. For ATC subjects without CNS and neck disease at baseline, subsequent brain and neck imaging should only be performed as clinically indicated.
2. Optional: Whole body PET/CT scan
3. MRI of the brain with contrast is mandated in this cohort; CT scan is not permitted. Please refer to imaging details in the SPM.
4. For NSGCT/NGGCT subjects *without* CNS disease at baseline, subsequent MRI of the brain with contrast should only be performed as clinically indicated (e.g., symptoms suggestive of CNS progression). For subjects with CNS disease at baseline, a MRI of the brain with contrast is required every 4 to 8 weeks or as clinically indicated. In addition, in order to confirm a CR in a subject with brain disease at baseline, a MRI of the brain with contrast must be performed 1 week prior to the first set of images showing CR to 4 weeks after the next protocol specified assessment.

Post-Baseline Assessments: All post-baseline assessments require imaging of disease sites identified by baseline scans. The same imaging modality used at baseline should be utilized for all post-baseline assessments. If subject discontinues treatment prior to Week 48 for reasons other than disease progression, disease assessments (imaging) should continue every 12 weeks until a new treatment is initiated.

Histology	Area(s) of Assessment	Imaging to be Performed	Alternative Imaging Methods if Contraindications are Present
ATC	Chest/Abdomen (including liver and adrenal glands)	CT scan ¹	N/A
BTC, ASI	Chest/Abdomen/Pelvis	CT scan with contrast	CT scan without contrast of the Chest and MRI with contrast of Abdomen/Pelvis
WHO Grade 1-4 Glioma	Brain	MRI with contrast ²	N/A
NSGCT/NGGCT, GIST	Chest/Abdomen/Pelvis	CT scan with contrast	CT scan without contrast of the Chest and MRI with contrast of Abdomen/Pelvis

Abbreviations: ASI, adenocarcinoma of small intestine; ATC, anaplastic thyroid carcinoma; BTC, biliary tract carcinoma; CT, computed tomography; GIST, gastrointestinal stromal tumor; MRI, magnetic resonance imaging; NGGCT, non-geminomatous germ cell tumor; NSGCT, non-seminomatous germ cell tumor; SPM, Study Procedures Manual; WHO, World Health Organization

1. Optional: Whole body PET/CT scan
2. MRI with contrast is mandated in this cohort; CT scan is not permitted. Please refer to imaging details in SPM.

7.5.1.1 Response Criteria for Solid Tumor Histologies

For solid tumor types (ATC, BTC, GIST, NSGCT/NGGCT, WHO Grade 1 and 2 gliomas, WHO Grade 3 and 4 gliomas and ASI), response evaluations will be determined according to the response assessment criteria listed in [Table 7](#).

Table 7 Response Criteria for Solid Tumor Histologies

Histology	Response Criteria	Response Subcategories defined as 'Response' ⁴
ATC, BTC, GIST, ASI, NSGCT/NGGCT	RECIST v 1.1 ¹	CR, PR
WHO Grade 1 and 2 Glioma	RANO Response Criteria: Response Assessment Criteria for WHO Grade 1 and 2 Glioma ²	CR, PR and MR

WHO Grade 3 and 4 Glioma	RANO Response Criteria: Updated Response Assessment Criteria for WHO Grade 3 and 4 Glioma ³	CR, PR
--------------------------	--	--------

Abbreviations: ATC, anaplastic thyroid carcinoma; BTC, biliary tract cancer; CR, complete response; GIST, gastrointestinal stromal tumor; MR, minor response; NGGCT, non-geminomatous germ cell tumor; NSGCT, non-seminomatous germ cell tumor; PR, partial response; RANO, Response Assessment in Neuro-Oncology; RECIST, Response Evaluation Criteria in Solid Tumors; SPM, Study Procedures Manual; WHO, World Health Organization

1. Refer to [Appendix 10](#) for details response criteria.
2. Refer to [Appendix 13](#) for details response criteria
3. Refer to [Appendix 14](#) for details response criteria
4. Serum tumor markers normalization will not be considered as part of response criteria.

7.5.2 Disease Assessment for Histologies of Hematologic Malignancies

For hematologic malignancies (HCL and MM), disease assessment will be conducted as noted below. For subjects whose disease may be followed by well-characterized tumor markers, disease assessment should also include results of tumor marker measurements. Disease assessments will be completed as indicated in the Time and Events Table (Section [7.1](#)).

7.5.2.1 Laboratory and Disease Assessments: HCL

Baseline Assessments: The following baseline disease assessments will be performed at the time points indicated in the Time and Event Table (Section [7.1](#)):

- Complete blood count
- Routine stain of peripheral blood sample
- **BM aspirate** and biopsy sample with H/E stain and IHC
- Flow cytometry on BM aspirate sample and peripheral blood sample
- Chest CT scan and abdominal CT scan with contrast

NOTE: MRI of the abdomen may be performed if abdominal CT cannot be performed. The method used to document baseline status is used consistently throughout the study to facilitate comparison of results.

If lymph nodes and spleen were enlarged at baseline, they must be followed by post-baseline assessments using a consistent imaging modality.

Post-Baseline Assessments: A response is to be determined every 4 weeks (+/-3 days) for the first 48 weeks of study treatment. Beyond 48 weeks, patients tolerating study drug in the judgement of the treating investigator may transition to a response assessment evaluation interval of at least every 12 weeks (+/-3 days) (Changed from “at least every 8 weeks (+/- 3 days)” indicated in Protocol Amendments 8 through 11). Patients that are not tolerating study drug in the judgement of the treating investigator must continue (or return to) response assessment evaluation every 4 weeks (+/-3 days). Assessments must be collected in agreement with those required in the response criteria (please consult Appendix 12).

- Complete blood count
- Routine stain of peripheral blood sample
- BM aspirate and biopsy sample with H/E stain and IHC
- Flow cytometry on BM aspirate sample will be performed as indicated in the Time and Event Table (Section [7.1](#)).

- Flow cytometry on peripheral blood sample will be performed as indicated in the Time and Event Table (Section 7.1)
- If lymph nodes and/or spleen were enlarged at baseline, they must be followed by post-baseline assessments using a consistent imaging modality as indicated in the Time and Event Table (Section 7.1).

7.5.2.2 Laboratory and Disease Assessment: MM

Baseline Assessments: The following baseline disease assessments will be performed at the time points indicated in the Time and Event Table (Section 7.1):

- Skeletal surveys
- Extramedullary disease assessment BM aspirate and biopsy samples: Samples will be assessed by IHC, flow cytometry, fluorescence *in situ* hybridization (FISH) and cytogenetics.
- UPEP
- SPEP
- CRP, β -2 microglobulin, serum FLC assay, levels of immunoglobulin (Ig)G, IgA, and IgM

Post-baseline Assessments: All post-baseline assessments require imaging of disease sites identified by baseline scans. The same imaging modality used at baseline should be utilized for all post-baseline assessments.

- BM aspirate and biopsy samples will be performed and assessed as indicated in the Time and Event Table (Section 7.1)
- Laboratory tests (SPEP, UPEP, CRP, β -2 microglobulin, serum FLC assay, levels of IgG, IgA, and IgM will be performed as indicated in the Time and Event Table (Section 7.1).
- Skeletal surveys: Post-baseline assessments only need to be performed if disease is noted on the baseline assessment. If no disease is identified at baseline, then subsequent skeletal surveys are only required if clinically indicated.
- Extramedullary disease assessment: Post-baseline assessments only need to be performed if disease is noted on the baseline assessment. If no disease is identified at baseline, then subsequent assessments are only required if clinically indicated.

7.5.2.3 Response Criteria for Hematologic Histologies

For hematologic malignancies (HCL and MM), response evaluations will be determined according to the response assessment criteria listed in Table 8.

Table 8 Response Criteria for Hematologic Histologies

Histology	Response Criteria	Response Subcategories defined as 'Response'
HCL	Adapted from NCCN guidelines, Consensus Resolution Criteria and previous studies definition ¹	CR \pm MRD, PR

MM	IMWG Uniform Response Criteria for MM ²	sCR, CR, PR, VGPR
----	--	-------------------

Abbreviations: CR, complete response; HCL, hairy cell leukemia; IMWG, International Myeloma Working Group; MM, multiple myeloma; MRD, minimal residual disease; NCCN, National Comprehensive Cancer Network; PR, partial response; sCR, stringent complete response; SPM, Study Procedures Manual; VGPR, very good partial response

1. Refer to [Appendix 12](#) for details on response criteria.
2. Refer to [Appendix 15](#) for details on response criteria.

8 DOSE MODIFICATIONS AND STOPPING CRITERIA

8.1 Dose Modification

General guidelines regarding management and dose reduction for AEs that are considered by the investigator to be related to study treatment and for which specific guidelines do not apply are provided in [Table 11](#). A maximum of two trametinib dose level reductions are allowed. If a third dose level reduction is required, study treatment should be permanently discontinued.

If a dose reduction of trametinib is required, but the toxicity resolves and no additional toxicities are seen after **one** treatment cycle (**4 weeks**), the dose of trametinib may be re-escalated but should not exceed 2 mg once daily.

If a dose reduction of dabrafenib is required, but the toxicity resolves and no additional toxicities are seen after one treatment cycle (4 weeks), the dose of dabrafenib may be re-escalated but should not exceed 150 mg BID daily.

These guidelines are intended primarily for toxicities not easily managed with routine supportive care. For example, alopecia is not an indication for dose modification, nor is Grade 2 nausea and vomiting that can be easily managed with anti-emetics.

These are general guidelines and investigators should always use clinical judgment in determining dose adjustments for any individual subject. Some toxicities may require hospitalization for stabilization, additional work-up, and consultation with a specialist before treatment can be restarted. Investigators should always err on the side of caution in these settings if treatment-related toxicity is a possibility.

Dose delay: Treatment with dabrafenib and trametinib may be delayed for up to 21 days to allow resolution of toxicity, or based on investigator discretion (e.g., scheduling issues). If the investigator and the Medical Lead conclude that continued treatment will benefit a subject who has experienced a treatment delay >21 days, then the subject may continue treatment with the approval of the Medical Lead. If a dose delay continues for 60 or more days, then both study treatments (dabrafenib and trametinib) will be permanently discontinued. Subjects should complete the Follow-Up Visit and then proceed to the extended follow-up phase as indicated in the Time and Events Table (Section 7.1).

Dose reduction: A dose reduction below 75 mg BID for dabrafenib or below 1 mg once daily for trametinib is not allowed. If a dose reduction below 75 mg BID for dabrafenib is required, dabrafenib will be permanently discontinued, but the subjects will be allowed to continue treatment with trametinib. If a dose reduction below 1 mg once daily for trametinib is required, then trametinib will be permanently discontinued, but these subjects will be allowed to continue treatment with dabrafenib.

If both study treatments are reduced below the minimum dose levels (75 mg BID for dabrafenib and 1 mg once daily for trametinib), then both study treatments will be permanently discontinued. Subjects should complete the Follow-Up Visit and then proceed to the extended follow-up phase as indicated in the Time and Events Table (Section 7.1).

For Grade 2 or 3 laboratory abnormalities that are considered unrelated to the study treatment or those that are reversible in <48 hrs (except for liver enzymes) such as electrolyte abnormalities may continue without dose reductions.

Dose Escalation: Following a dose reduction, subjects may be re-escalated to a higher dose level with the approval of the Medical Lead. If the AE has resolved to Grade 1 or baseline at the reduced dose level, and no additional toxicities are seen after 4 weeks of study treatment at the reduced dose, the dose may be increased to the previous dose level.

Table 9 describes the dose /schedule to be used for any necessary dose modifications (based on the initial dose level of 150 mg BID) for dabrafenib.

Table 9 Dabrafenib Dose Levels

Dose Level	Dose/Schedule
0	150 mg BID
-1 (first dose reduction)	100 mg BID
-2 (second dose reduction)	75 mg BID

Table 10 describes the dose /schedule to be used for any necessary dose modifications (based on the initial dose level of 2 mg once daily) for trametinib.

Table 10 Trametinib Dose Levels

Dose Level	Dose/Schedule
0	2 mg once daily
-1 (first dose reduction)	1.5 mg once daily
-2 (second dose reduction)	1 mg once daily

Table 11 Dose Modification Guidelines – General

CTCAE Grade	Action and Dose Modification ^{1,2}
Grade 1 or Grade 2 (Tolerable)	
Any occurrence	
 Continue treatment with dabrafenib and trametinib at same dose level (no dose modification)
Grade 2 (Intolerable) or Grade 3	
1 st , 2 nd or 3 rd occurrence	
 Interrupt dabrafenib and trametinib until toxicity resolves to ≤ Grade 1 then restart at next lower dose level
4 th or greater occurrence	
 Discontinue treatment with dabrafenib and trametinib
Grade 4	

1 st occurrence	
 Interrupt dabrafenib and trametinib until toxicity resolves to ≤ Grade 1 or baseline then restart at next lower dose level or discontinue at the discretion of the investigator
2 nd occurrence	
 Interrupt dabrafenib and trametinib until toxicity resolves to ≤ Grade 1 or baseline then restart at 2 dose levels lower than the starting dose or discontinue at the discretion of the investigator and after discussion with the Medical Lead.
3 rd occurrence	
 Discontinue treatment with dabrafenib and trametinib

- Treatment should be discontinued if more than 2 dose reductions are required
- Approval from the Medical Lead is required to restart study treatment after ≥21 days

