6 STUDY TREATMENTS

The term ‘study treatment’ is used throughout the protocol to describe any combination of IP received by the subject as per the protocol design. Study treatment may therefore refer to the individual study treatments or the combination of those study treatments.

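### Protocol Section 8.1: the Table 11 instruction for a third intolerable Grade 2 or Grade 3 occurrence conflicts with the two available dose reductions and with the table's own footnote, and the text does not say whether one drug or both must stop

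*Protocol*

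**What the plan says.** Four pieces of Protocol Section 8.1 bear on a third reduction.

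- **Opening paragraph.** "A maximum of two trametinib dose level reductions are allowed". The next sentence reads: "If a third dose level reduction is required, study treatment should be permanently discontinued".
- **Paragraph on dose reduction.** "A dose reduction below 75 mg BID for dabrafenib or below 1 mg once daily for trametinib is not allowed". If dabrafenib would have to go below its minimum, "dabrafenib will be permanently discontinued, but the subjects will be allowed to continue treatment with trametinib". If trametinib would, "then trametinib will be permanently discontinued, but these subjects will be allowed to continue treatment with dabrafenib". Both drugs stop only when both would fall below their minimums.
- **Tables 9 and 10.** Each drug has a starting level and two reduced levels: 150, 100 and 75 mg BID for dabrafenib; 2, 1.5 and 1 mg once daily for trametinib.
- **Table 11, row for intolerable Grade 2 or Grade 3.** At each of the first three occurrences both drugs are interrupted until recovery, "then restart at next lower dose level". Discontinuation of both comes at the fourth occurrence or later. Footnote 1, attached to the heading of the action column, says: "Treatment should be discontinued if more than 2 dose reductions are required".

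Section 8.1 also allows re-escalation after four weeks without further toxicity, with the Medical Lead's approval. On terminology, Protocol Section 6 says: "Study treatment may therefore refer to the individual study treatments or the combination of those study treatments". SAP Section 2.1.1 likewise uses the term for either drug. Protocol Section 4.1 allows the remaining drug to be given alone when the other is stopped.

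**The concern.** A site managing a third intolerable Grade 2 or Grade 3 event under Table 11 meets a row that says restart lower and a footnote that can say stop. If the subject is already at level -2, the row points to a dose that the protocol does not permit. If the site then looks to the opening paragraph, it learns that study treatment stops, but not whether that means one drug or both.

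The choice cannot be undone. Protocol Section 16.2 bars retreatment after permanent discontinuation, and eligibility required that subjects have no standard treatment option. Section 4 rules out waivers except for immediate safety concerns. This is therefore first a patient-management matter. For the analysis, SAP Section 2.3.3 tabulates discontinuation and number of reductions separately for each drug, and those tables would reflect how each site read the text.

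**Working it through.** This is a check of consistency between texts; the plan states no figure to reproduce.

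**Step 1. Levels needed against levels available.** Tables 9 and 10 give two reduced levels per drug (-1 and -2). The Table 11 row allows three restarts, each one level lower. With no re-escalation: 0 - 1 = -1; -1 - 1 = -2; -2 - 1 = -3. Level -3 is absent from both tables and below the floor.

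**Step 2. Allow re-escalation.** Assume that the subject starts at level 0, both drugs move together, any re-escalation is one level, and no other event causes a reduction. The four possible sequences are:

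| Re-escalated after occurrence 1 / 2 | Level after occurrences 1, 2, 3 | Third level exists? | Reductions made | Levels below start at occurrence 3 |
|---|---|---|---|---|
| no / no | -1, -2, -3 | no | 3 | 3 |
| no / yes | -1, -2, -2 | yes | 3 | 2 |
| yes / no | -1, -1, -2 | yes | 3 | 2 |
| yes / yes | -1, -1, -1 | yes | 3 | 1 |

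**Step 3. Apply footnote 1 (discontinue above 2).**

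- Counted as reductions made, the figure is 3 in every sequence. The footnote says stop in all four, where the row says restart.
- Counted as levels below the starting dose, the figure exceeds 2 only in the first sequence. There the footnote says stop and the row says restart; in the other three they agree.

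So without re-escalation the row and the footnote disagree on either count. With re-escalation they disagree on one count and not on the other, and the text does not say which count is meant.

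**Step 4. Grade 4 rows, for comparison.** These restart at -1, then at -2 (either restart may be replaced by discontinuation), and stop at the third occurrence. They need two reduced levels, and two exist. The problem is confined to the row for intolerable Grade 2 or Grade 3.

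**Step 5. One drug or both.** Two readings of the opening paragraph:

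- Study treatment means trametinib. The paragraph then agrees with the later one, under which trametinib stops and dabrafenib may continue.
- Study treatment means both drugs. It then conflicts with that later paragraph.

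Section 6 permits either meaning, so the definition does not decide. The word treatment in footnote 1 has the same gap.

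**The case against.** A reader might infer that Section 8.1 gives three mutually incompatible instructions: stop everything, stop one drug, or restart at a missing level. The documents do not support that much.

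- The opening sentence follows directly on a sentence about trametinib alone, and Section 8.1 names both drugs elsewhere when it means both. Read as trametinib only, it agrees with the paragraph on dose reduction and with Section 4.1. What stands is an unstated scope, with a conflict under one reading only.
- Footnote 1 sits on the column heading and so qualifies the row. Table 11 contradicts itself rather than plainly ordering a dose that does not exist.
- The row counts occurrences, not levels, and re-escalation can leave a level available. Tables 9 and 10 label their levels as first and second reductions, so the footnote can fairly be read as referring to levels below the start. On that reading the row works after a re-escalation. It still does not work without one.
- Table 11 is general guidance for related events that have no specific rule, and Section 8.1 leaves room for clinical judgment. That limits its reach but does not tell a site which of two opposite actions the protocol intends.

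A reader might also infer harm to the efficacy analyses. That is not shown. Stopping treatment does not itself censor: Protocol Section 16.3 continues disease assessments until progression or new therapy, and SAP Section 2.4.3 uses response assessments made after treatment ends. Whether one drug or both stop, the combination ends at the same point, so its duration does not depend on that question. A subject is likewise counted among those with an adverse event leading to discontinuation of any study treatment under both readings.

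**Conclusion.** The concern holds in a limited form. For a subject with three intolerable Grade 2 or Grade 3 occurrences and no re-escalation, the Table 11 row cannot be followed as written: it needs a third reduced level where two exist, against the dose floor and against its own footnote. After a re-escalation, whether row and footnote conflict depends on a counting rule that the protocol does not give. It is also unstated, in the opening paragraph and in the footnote, whether one drug or both must stop.

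The size in subjects is unknown. Amendment 11 reports 55 subjects on treatment on 06-Apr-2020, but that is everyone then on treatment, not those facing a third reduction. No effect on progression-free survival or duration of response is shown. The conclusion rests on the level count in Tables 9 and 10 and on the assumptions listed with the sequences. It takes no position on which rule is clinically right.

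**What to change.** Reconcile four texts in Protocol Section 8.1 into one instruction: the opening paragraph, the paragraph on dose reduction, the third-occurrence part of the Table 11 row for intolerable Grade 2 or Grade 3, and footnote 1. In doing so:

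1. State for each of them whether dabrafenib, trametinib or both are meant.
2. State how reductions are counted after a re-escalation: reductions made, or levels below the starting dose.
3. Check that the row, the footnote and Tables 9 and 10 then give the same action for each of the four sequences above.

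The sponsor's clinical team decides which rule applies. The cost is clarifying text in the protocol; this reconciliation by itself calls for no change to sample size, endpoints or analysis methods.

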SYSTEM Adequate Baseline Organ Function	TEST	Histology	LABORATORY VALUES¹
	Total Bilirubin ⁴	BTC	≤3 times ULN if stable for 14 days prior to enrollment
		GIST, WHO Grade 1-4 Glioma, NSGCT/NGGCT, MM	≤2 times ULN
		HCL	<3 times ULN
		ASI	≤2 times ULN OR ≤3 times ULN if stable for 14 days prior to enrollment for ampullary and periampullary carcinoma
	ALT and AST ⁵	ATC, GIST, NSGCT/NGGCT	≤2 times ULN without liver metastases ≤2.5 times ULN if documented liver metastases
		BTC, ASI, MM	≤3 times ULN without liver metastases ≤5 times ULN if documented liver metastases
		HCL	<5 times ULN
		WHO Grade 1, 2, 3 or 4 Glioma	≤3 times ULN
Renal	Creatinine	ATC, BTC, GIST, WHO Grade 1-4 Glioma, NSGCT/NGGCT, ASI, HCL, MM	≤1.5 mg/dL
	OR Calculated Creatinine Clearance ⁶ or 24-hr Urine Creatinine Clearance	ATC, BTC, GIST, WHO Grade 1-4 Glioma, NSGCT/NGGCT, ASI, HCL, MM	≥50 mL/min
Cardiac	LVEF	ATC, BTC, GIST, WHO Grade 1-4 Glioma, NSGCT/NGGCT, ASI, HCL, MM	≥LLN ⁷ by ECHO

Abbreviations: ALT, alanine aminotransferase; ANC, absolute neutrophil count; ASI, adenocarcinoma of small intestine AST, aspartate aminotransferase; CBC, complete blood count; ECHO, echocardiogram; HCL, hairy cell leukemia; hr, hour; INR, international normalization n ratio; LLN, lower limit of normal; LVEF, left ventricular ejection fraction; PT, prothrombin time; PTT, partial thromboplastin time; ULN, upper limit of normal

- Laboratory values are obtained within 14 days prior to first dose of study treatment.
- PTT and PT/INR >1.5 times ULN will be acceptable in case of subjects receiving therapeutic anticoagulants such as warfarin as long as INR is monitored during the study according to clinical practice.
- HCL: No minimum CBC criteria if the cytopenias are due to disease under study.
- HCL: Subjects will be allowed to enroll with indirect hyperbilirubinemia; however, this condition must be confirmed due to hemolysis, hypersplenism or direct bilirubin ratio <35%, and requires approval from the Medical Lead.
- HCL: Subjects will be allowed to enroll with elevated ALT/AST values up to 5 times ULN; however this condition must be confirmed due to hemolysis and/or hypersplenism and not associated with hepatic dysfunction and required approval from the Medical Lead.
- Calculated by the Cockcroft-Gault formula (see [Appendix 3](#)).
- If LLN is not defined for a given institution, then ejection fraction must be ≥ 50%.

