 - Brain metastases (*except* for subjects in the WHO Grade 1 or 2 Glioma or WHO Grade 3 or 4 Glioma histology cohorts) that are symptomatic or untreated or not stable for ≥ 3 months (must be documented by imaging) or requiring corticosteroids. Subjects on a stable dose of corticosteroids > 14 days and have not required treatment with enzyme-inducing anticonvulsants for >30 days prior to enrollment can be enrolled with approval of the Medical Lead.
 - Symptomatic or untreated leptomeningeal or spinal cord compression
NOTE: Subjects who have been previously treated for these conditions and have stable CNS disease (documented by consecutive imaging studies) for >60 days, are asymptomatic and currently not taking corticosteroids, or have been on a stable dose of corticosteroids for at least 30 days prior to enrollment, are permitted.
 - Interstitial lung disease or pneumonitis
 - Any unresolved \geq Grade 2 (per Common Terminology Criteria for Adverse Events [CTCAE] version 4.0) toxicity from previous anti-cancer therapy at the time of enrollment, except alopecia or Grade 2 anemia
NOTE: Subjects with MM who have \leq Grade 2 peripheral neuropathy (per CTCAE v4.0) are permitted.
 - Any serious and/or unstable pre-existing medical disorder, psychiatric disorder, or other conditions that could interfere with subject's safety, obtaining informed consent or compliance to the study procedures
8. History of RVO

9. Clinically significant GI abnormalities that may alter absorption such as malabsorption syndrome or major resection of the stomach or bowels. For example, subjects should have no more than 50% of the large intestine removed and no sign of malabsorption (i.e., diarrhea).

NOTE: If clarification is needed as to whether a condition will significantly affect the absorption of study treatments, contact the Medical Lead.

10. History or evidence of cardiovascular risk including any of the following:

- Acute coronary syndromes (including myocardial infarction and unstable angina), coronary angioplasty, or stenting within 6 months prior to enrollment

- Clinically significant uncontrolled arrhythmias

NOTE: Subjects with controlled atrial fibrillation for >30 days prior to enrollment are eligible.

- Class II or higher congestive heart failure as defined by the New York Heart Association (NYHA) criteria ([Appendix 2](#))

- Left ventricular ejection fraction (LVEF) below the institutional LLN

NOTE: If a LLN does not exist at an institution, then use LVEF <50%.

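### Table 11 gives intolerable Grade 2 and Grade 3 toxicities no baseline alternative for restart, although its Grade 4 rows have one and some subjects may enter above Grade 1

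*Protocol*

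**What the plan says.** Table 11 in Protocol Section 8.1 covers adverse events that the investigator considers related to study treatment and that have no specific guideline of their own.

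- First to third intolerable Grade 2 or Grade 3 event: "Interrupt dabrafenib and trametinib until toxicity resolves to ≤ Grade 1 then restart at next lower dose level".
- First Grade 4 event: "Interrupt dabrafenib and trametinib until toxicity resolves to ≤ Grade 1 or baseline then restart at next lower dose level", or discontinue at the investigator's discretion.
- Second Grade 4 event: interrupt until the toxicity is "≤ Grade 1 or baseline then restart at 2 dose levels lower than the starting dose", or discontinue after discussion with the Medical Lead.

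Other rules accept baseline as well. The QTc rule in Table 12 uses Grade 1 or baseline, and the re-escalation text of Section 8.1 begins "If the AE has resolved to Grade 1 or baseline at the reduced dose level".

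Two further provisions matter. On delays, Section 8.1 says: "If a dose delay continues for 60 or more days, then both study treatments (dabrafenib and trametinib) will be permanently discontinued". On entry, item 7 of Section 5.4.2 excludes unresolved Grade 2 or higher "toxicity from previous anti-cancer therapy at the time of enrollment, except alopecia or Grade 2 anemia", and a note there permits neuropathy up to Grade 2 in multiple myeloma (MM). Footnote 3 of Table 3 in Section 5.4.1 adds: "HCL: No minimum CBC criteria if the cytopenias are due to disease under study".

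**The concern.** One table states the resolution test in two ways. The form without the baseline alternative is attached to the less severe events. Because the alternative is written into the rows directly below, a site cannot safely assume that it is implied in the Grade 2/3 row.

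This matters only for a subject whose baseline is above Grade 1, and the protocol knowingly admits some. For them, full recovery to the entry state and resolution as printed are different things. What is at stake is who stays on treatment. Section 16.2 does not allow retreatment after permanent discontinuation. SAP Section 2.7.1 summarizes adverse events leading to permanent discontinuation of any study treatment, so a subject stopped in this way could appear in that table although the event had returned to baseline.

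**Working it through.** No sample size, error rate or event count is involved, and the plan states no figure to reproduce. The check sets the rules side by side and follows one subject through them.

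**Inputs**

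| Rule | Place in the protocol | Resolution test |
|---|---|---|
| Intolerable Grade 2 or Grade 3, 1st to 3rd event | Table 11 | Grade 1 or less |
| Grade 4, 1st event | Table 11 | Grade 1 or less, or baseline |
| Grade 4, 2nd event | Table 11 | Grade 1 or less, or baseline |
| QTc prolongation | Table 12 | Grade 1 or baseline |
| Re-escalation after a reduction | Section 8.1 | Grade 1 or baseline |

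The last line governs a later decision, taken after 4 weeks at a reduced dose. It shows how the section words resolution elsewhere; it is not itself a restart rule.

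**Subject followed:** enrolled with Grade 2 anemia from earlier therapy, or with MM and Grade 2 neuropathy.

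1. While the condition is stable and tolerable, Table 11 asks for no dose change. The problem needs a related event severe enough to interrupt treatment.
2. A related worsening to Grade 3 interrupts both drugs. The subject returns to Grade 2, which is baseline. Grade 2 is not Grade 1 or less, so the test as printed is not met.
3. Had the worsening reached Grade 4, return to the same Grade 2 baseline would have met the test.
4. In step 2 the delay continues. After about 21 days (more than 21 in the text, 21 or more in the Table 11 footnote), continuing needs Medical Lead approval. At 60 days both drugs stop permanently.

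**Other places that might supply the missing criterion**

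- The laboratory exemption in Section 8.1 covers Grade 2 or 3 abnormalities that are unrelated or reverse in under 48 hours. A persistent related event fits neither.
- The dose-modification section has no specific table for anemia, other cytopenias or neuropathy, so Table 11 is the rule that applies.
- Alopecia is also excepted at entry, but Section 8.1 says that it is no reason to modify dose. Anemia and MM neuropathy are therefore the clear examples.
- In hairy cell leukemia (HCL), inclusion criterion 3 requires at least one of symptomatic splenomegaly or a low hemoglobin, platelet or neutrophil count. Cytopenia is thus part of how that cohort is selected. The CTCAE cut-offs for counts are not in the documents, so no grade is assigned to those limits here.

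**The case against.** The strongest answer is that the protocol, read as a whole, lets return to baseline count as resolution. Table 11 concerns related toxicity only. Section 11.1 leaves out of the adverse event definition fluctuations of a pre-existing condition that do not worsen, and Section 11.3 treats findings tied to the underlying disease in a similar way. Section 7.4.8 repeats abnormal laboratory values until they are normal or back to baseline. Section 10.1 permits transfusion. Section 8.1 calls these general guidelines and tells investigators to use clinical judgment.

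Much of this stands, and it rules out two stronger readings. A reader might infer that such a subject has no way back to treatment. The judgment clause and the Medical Lead's approval mean that the documents do not support this. A reader might also infer that the stopping path counts existing disease in place of drug toxicity. It does not: it starts only from an event considered related.

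It does not remove the point. None of these provisions defines resolution for the Grade 2/3 row. Medical Lead approval deals with the length of the delay. The 60-day rule is worded as mandatory, and Section 4 rules out waivers except for immediate safety concerns.

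Two other objections are right as far as they go. Taken over the whole pathway, Grade 4 is handled more strictly: discontinuation is an option from the first event, and the third event ends treatment, against the fourth for intolerable Grade 2 or Grade 3. Only the resolution test runs the other way. And the CTCAE grade determines which row applies, so sites do not choose between rows; any variation between them would come from how they read the Grade 2/3 row.

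**Conclusion.** The point holds as an inconsistency in wording with a possible effect on treatment continuation. Read literally, the Grade 2/3 row has a stricter resolution test than the Grade 4 rows for any subject whose permitted baseline is above Grade 1, and the 60-day rule can then end treatment with both drugs.

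This rests on two assumptions: that the absence of the baseline alternative from the Grade 2/3 row is meaningful, since neighboring rows contain it; and that a site applies the row as printed without using the judgment clause.

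Its size cannot be given. The documents do not say how many subjects entered above Grade 1 or had an interruption of this kind. The Amendment 11 rationale reports 36 HCL subjects among the 55 still on treatment at 06-Apr-2020, and a reader might take this as the number at risk. It is not: it counts subjects retained on treatment, and gives neither their baseline grades nor any discontinuation from this cause. A reader might also infer a loss of response or of its duration, but nothing in the documents quantifies one.

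A clarification should be made, because the rule bears on who stays on treatment and the change is small.

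**What to change.** Reconcile the Grade 2 (Intolerable)/Grade 3 row of Table 11 with the Grade 4 rows of the same table and with the entry criteria in Sections 5.4.1 and 5.4.2. State how resolution is assessed for an abnormality that was already above Grade 1 and permitted at entry, and how that assessment relates to the 60-day rule. If the difference between the rows is intended, say so and give the reason. The restart and re-escalation rules need not be identical, and this review does not say which criterion is right.

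The cost is wording in Table 11 or a footnote to it. No procedures or data are added.
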